#### **6.6.5. Height & Weight Measurement**

Height and weight measurement will be collected at all study visits. The difference in body weight and height measurements between Day 1 and End of treatment, post-treatment Week 12, and post-treatment Week 24 will be calculated.

#### **6.6.6. Bone Age Assessment**

A single X-ray of the left wrist, hand, and fingers will be performed at Day 1 Visit and post-treatment Week 24. Local radiologist will determine the bone age from x-ray.

#### **6.6.7. Swallowability Assessment**

A SOF Swallowability Assessment will be performed at screening up to Day 1. Subjects who have indicated that they can take pills will be observed taking a placebo for the 400 mg SOF tablet. This will confirm the swallowability of the 400 mg tablet size. If, a subject is unable to swallow the 400 mg tablet size he/she will repeat the assessment with a placebo for the 100 mg SOF tablet. If unable to take the 100 mg SOF tablet, the subject will be dispensed the SOF oral granule formulation.

#### **6.6.8. Vital Signs**

Assessment of vital signs will include measurement of resting blood pressure, pulse, respiratory rate, and temperature.

Blood pressure will be measured using the following standardized process:

- Subject should sit for  $\geq 5$  minutes with feet flat on the floor and measurement arm supported so that the midpoint of the manometer cuff is at heart level;
- Use a mercury sphygmomanometer or automatic blood pressure device with an appropriately sized cuff with the bladder centered over the brachial artery;
- Measure and record the blood pressure to the nearest 2 mmHg mark on the manometer or to the nearest whole number on an automatic device.

#### **6.6.9. Body Mass Index (BMI)**

BMI is calculated by the following equation.

$$\text{BMI} = \frac{\text{weight (pounds)} \times 703}{(\text{height in inches})^2} \quad \text{or} \quad \frac{\text{weight in kilograms}}{(\text{height in meters})^2}$$

#### **6.6.10. Estimated Glomerular Filtration Rate (GFR)**

Estimated Glomerular Filtration Rate (GFR) using Schwartz Formula ( $\text{mL}/\text{min}/1.73\text{m}^2$ )  
 $= k \times L/\text{Scr}$  [(k is a proportionality constant, for adolescent females  $\geq 12$  years old is 0.55; for adolescent males  $\geq 12$  years old is 0.70, and for children 3- <12 years old is 0.55); L is height in centimeters (cm); and  $S_{\text{cr}}$  is serum creatinine (mg/dL)]

#### **6.6.11. Viral Sequencing (Archive)**

Plasma samples will be collected at Day 1 and each visit for viral sequence analysis. Unused samples may be archived.

#### **6.6.12. Pregnancy Testing**

All females of childbearing potential will have urine pregnancy testing every 4 weeks during the dosing period and for a minimum of 6 months following the last dose of RBV. If required by local regulations, additional pregnancy tests beyond 6 months may be added. In the event of a positive urine pregnancy result, subjects will be instructed to stop study drugs immediately and return to the clinic as soon as possible for a serum pregnancy test.

Pregnancy test kits will be dispensed to female subjects of child bearing potential at the 4-Week Post-Treatment visit. The subject will be contacted by telephone monthly to confirm that urine pregnancy testing has been performed post-treatment and to record the outcome.

Alternatively, if required by local regulations or preferred by the investigator or subject, the subject may return to the clinic for urine pregnancy tests.

#### **6.6.13. Quality of Life Survey (PedsQL™)**

The **PedsQL™** Pediatric Quality of Life Inventory V4.0 Short Form (SF15) will be completed at Day 1, End of Treatment (Week 12 for GT-2 subjects, Week 24 for GT-3 subjects, or at Early Termination, if applicable), 12-Week Post-Treatment, and 24-Week Post-Treatment visits.

The **PedsQL™** has separate survey instruments administered by age group, including the Teen Report (ages 13-18), Child Report (ages 8-12), Young Child Report (ages 5-7), and Toddlers (ages 2-4). Each survey accompanied by the respective parent proxy survey will be administered to the subject and their parent/legal guardian (with the exception of the Toddlers Report which will only be completed by the parent/guardian) for the current age group at the time of survey administration.

#### **6.6.14. SOF Granule Palatability Assessment**

A palatability assessment for the SOF granules will be performed at Day 1 to subjects receiving the granules.

## 7. TOXICITY MANAGEMENT

### 7.1. Modification of Dose/Schedule Due to Toxicity

Dose reduction of RBV due to toxicity should be performed according to the product label. Information is provided in [Table 7-1](#).

**Table 7-1. RBV Dose Reduction Guidelines**

Laboratory Values	Reduce RBV Dose by 200 mg/day if:	Discontinue RBV if:
Hemoglobin in subjects with no cardiac disease	<10 g/dL	<8.5 g/dL
Hemoglobin in subjects with history of stable cardiac disease	≥2 g/dL decrease in hemoglobin during any 4 week period treatment	<12 g/dL despite 4 weeks at reduced dose

Dose reduction in pediatric patients is accomplished by modifying the recommended RBV dose from original starting dose of 15 mg/kg daily in a two-step process to 12 mg/kg/day, then to 8 mg/kg/day, if needed.

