##### 3.1.1. PK Lead-in

The PK Lead-in Phase will evaluate and/or confirm the age appropriate SOF dose by analyzing PK, safety, and antiviral activity of SOF + RBV through 7 days of dosing for each cohort. Children aged 3 to < 6 years, children aged 6 to < 12 years, and adolescents aged 12 to < 18 years with GT-2 or GT-3 HCV infection and evidence of HCV RNA  $\geq$  1000 IU/mL at study entry will be evaluated. Subjects must be treatment naïve to participate in the PK Lead-in Phase. Three cohorts of up to 10 subjects each will be sequentially enrolled:

- Cohort 1: 12 to < 18 years old weighing  $\geq$  45kg
- Cohort 2: 6 to < 12 years old weighing  $\geq$  17kg and < 45 kg
- Cohort 3: 3 to < 6 years old

The study will start with Cohort 1. Subjects will receive SOF (400 mg adult tablet or 4 x 100 mg tablets if determined necessary based on SOF swallowability assessment) + RBV for 7 days with intensive PK conducted on Day 7.

Once Cohort 2 is opened, subjects will receive SOF 200 mg (4 x 50 mg capsules containing granules if determined necessary based on SOF swallowability assessment) + RBV for 7 days with intensive PK conducted on Day 7. Subjects who weigh outside of the  $\geq$  17kg and < 45 kg range will be excluded.

Once Cohort 3 is opened, subjects weighing  $\geq$ 17 kg will receive 200 mg SOF (4 x 50 mg capsules containing granules) + RBV for 7 days with intensive PK conducted on Day 7. Cohort 3 subjects weighing <17 kg will receive 150 mg SOF (3 X 50mg capsules containing granules) + RBV for 7 days with intensive PK conducted on Day 7.

Subjects enrolled in the PK Lead-in of each cohort (Cohorts 1, 2 and 3) will immediately enroll in the Treatment Phase as they complete Day 7 of PK Lead-in. They will continue dosing with SOF + RBV with no interruption of study drug administration. Subjects rolling over from the PK Lead-in Phase will not be required to perform the screening, Day 1 or Week 1 visit of the Treatment Phase.

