### 4.2. Inclusion Criteria

Subjects must meet *all* of the following inclusion criteria to be eligible for participation in this study.

1. Parent or legal guardian able to provide written informed consent prior to any screening evaluations and willing to comply with study requirements. Subjects will provide assent if possible.
2. 3 years to < 18 years of age (consent of parent or legal guardian required)
3. PK Lead-in only: subjects in Cohort 1 (age 12 to <18 years of age) must weigh  $\geq 45$  kg
4. PK Lead-in only: subjects in Cohort 2 (age 6 to <12 years of age) must weigh  $\geq 17$  kg and < 45 kg
5. PK Lead-in only: all subjects must be treatment naïve
6. Treatment experienced subjects: prior treatment failure to a regimen including interferon either with or without RBV that was completed at least 8 weeks prior to Baseline/Day 1.
7. Chronic HCV infection documented by either:
  - a) a positive anti-HCV antibody test or positive HCV RNA or positive HCV genotyping test at least 6 months prior to the Day 1 visit, or
  - b) a liver biopsy performed prior to the Day 1 visit with evidence of chronic HCV infection
8. Infection with HCV GT-2 or GT-3 as determined at Screening
9. HCV RNA  $\geq 1000$  IU/mL at Screening
10. Adequate hematologic function (absolute neutrophil count  $\geq 1,500/\text{mm}^3$ ; hemoglobin  $\geq 12$  g/dL for males and  $\geq 11$  g/dL for females.)
11. Negative serum  $\beta$ -HCG pregnancy test (for females of childbearing potential only, as defined in [Appendix 5](#))
12. Subject able to provide written assent, if they have the ability to read and write, as determined by IRB/IEC/local requirements and Investigator's discretion

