## 5.3.2. Dosage and Administration of RBV

RBV dose will be administered by weight as follows:

Body Weight kg (lbs.)	RBV Daily Dose	RBV Number of Capsules
<47 (<103)	15 mg/kg/day	Use Oral Solution. Divided dose in the morning and evening.
47-49 (103-108)	600 mg/day	1 x 200-mg capsules A.M. 2 x 200-mg capsules P.M.
50-65 (110 – 143)	800 mg/day	2 x 200-mg capsules A.M. 2 x 200-mg capsules P.M.
66-80 (145 – 176)	1000 mg/day	2 x 200-mg capsules A.M. 3 x 200-mg capsules P.M.
81-105 (178-231)	1200 mg/day	3 x 200-mg capsules A.M. 3 x 200-mg capsules P.M.
>105 (>231)	1400 mg/day	3 x 200-mg capsules A.M. 4 x 200-mg capsules P.M.

\* Note: Subjects with a body weight greater than or equal to 47 kg may utilize the RBV oral solution if necessary.

The morning dose of RBV will be taken with food and SOF. The evening dose of RBV will be taken with food.

RBV will be supplied by Gilead Sciences for all subjects.

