#### **5.4. Co-administration of SOF and RBV**

In the Treatment Phase of the study, each subject will be given instructions to maintain approximately the same daily dosing interval between study drug doses.

For **morning doses**, subjects will be instructed to take study drugs as follows:

- SOF
- Weight-based RBV (as per Section 5.3.2).

For **evening doses**, subjects will be instructed to take study drug as follows:

- Weight-based RBV (as per Section 5.3.2).

If a subject forgets to take the medication at the correct time, it may be taken later in the day; however, no more than the protocol specified dose of SOF should be taken on any calendar day. The subject should resume the standing dosing schedule on the next day. Study medications should not be cut or split.

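### Protocol Section 7.1 prints two unreconciled ribavirin reduction instructions: they give different doses at every weight under 47 kg, and below 13.3 kg the 200 mg/day cut exceeds the whole daily dose

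*Protocol*

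**What the plan says.** Protocol Section 7.1 opens with a deferral: "Dose reduction of RBV due to toxicity should be performed according to the product label". It then sends the reader to Table 7-1 for the information.

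Table 7-1 has an action column headed "Reduce RBV Dose by 200 mg/day if". For subjects without cardiac disease the trigger is haemoglobin below 10 g/dL, and a separate column discontinues RBV below 8.5 g/dL. The table limits neither column by age, weight or formulation, and does not say whether the 200 mg/day cut may be repeated.

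The sentence under the table covers pediatric patients and takes the dose down "from original starting dose of 15 mg/kg daily in a two-step process to 12 mg/kg/day, then to 8 mg/kg/day, if needed". It gives no haemoglobin trigger for the second step.

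Three other places determine who is affected:
- **Age.** Section 4.2, criterion 2, admits subjects "3 years to < 18 years of age".
- **Starting dose.** In Section 5.3.2, subjects under 47 kg start at 15 mg/kg/day with the direction "Use Oral Solution. Divided dose in the morning and evening". From 47 kg upwards the daily dose is flat, 600 to 1400 mg in 200 mg capsules, but "Subjects with a body weight greater than or equal to 47 kg may utilize the RBV oral solution if necessary".
- **Weight floor.** Section 3.1.1 defines the youngest group as "Cohort 3: 3 to < 6 years old". It splits that group at 17 kg for sofosbuvir dosing but sets no minimum.

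**The concern.** Two reduction rules stand next to each other, and no text says which subjects each one governs. The trial is entirely pediatric, so the table's column cannot be assigned to a separate adult group. The words about a 15 mg/kg starting dose hint that the sentence is meant for subjects under 47 kg, but the table is not switched off for them. For subjects of 47 kg or more, who do not start on 15 mg/kg, it is unclear whether the sentence applies.

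What is at stake is safety management in children. Two sites that follow the same page could give different RBV doses to similar children at the same haemoglobin. For the smallest children, a step called a reduction at below 10 g/dL would remove RBV entirely, although the same table reserves discontinuation for below 8.5 g/dL. Safety and tolerability is the primary objective of the Treatment Phase, and SAP Section 7.1.6 tabulates adverse events leading to RBV modification or interruption. The action behind those counts should be defined.

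**Working it through.** **Starting dose.** 15 mg/kg/day over 84 and 168 days gives 15 × 84 = 1,260 mg/kg and 15 × 168 = 2,520 mg/kg. These match the prescribed totals for subjects under 47 kg in SAP Section 4.2.2, so 15w mg/day is the correct starting dose for weight w (kg) in that band.

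**Formulas under 47 kg.**
- Start: 15w
- Table 7-1: 15w − 200
- Sentence: 12w at step 1, 8w at step 2

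**Where they meet.**
- Table equals step 1: 15w − 200 = 12w, so w = 200/3 = 66.7 kg. This is outside the band. Under 47 kg the table's result is always lower, by 200 − 3w, which is more than 200 − 141 = 59 mg/day.
- Table equals step 2: 15w − 200 = 8w, so w = 200/7 = 28.6 kg. Below this weight the table's cut leaves less than the sentence's lowest step.
- Table leaves nothing: 15w = 200, so w = 13.3 kg.

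**Examples (mg/day).**

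| Weight (kg) | Start | Table | Sentence step 1 | Sentence step 2 | Table cut, % of start |
|---|---|---|---|---|---|
| 13 | 195 | −5 | 156 | 104 | 102.6 |
| 16 | 240 | 40 | 192 | 128 | 83.3 |
| 17 | 255 | 55 | 204 | 136 | 78.4 |
| 20 | 300 | 100 | 240 | 160 | 66.7 |
| 30 | 450 | 250 | 360 | 240 | 44.4 |
| 40 | 600 | 400 | 480 | 320 | 33.3 |
| 45 | 675 | 475 | 540 | 360 | 29.6 |
| 46 | 690 | 490 | 552 | 368 | 29.0 |

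The sentence's first step is always 3/15 = 20% of the start. Across the Cohort 2 lead-in weight window (17 to <45 kg) the table's cut runs from about 78% to about 30%.

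**Rounding.** SAP Section 4.2.2 says weights were rounded to whole kilograms for RBV dosing. A measured weight just under 13.5 kg is then dosed as 13 kg (195 mg/day), so the point at which the cut exceeds the dose moves up slightly.

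**At 47 kg or more, only if the mg/kg sentence applies.** At 47 kg, 600 − 12 × 47 = 36 mg/day below the start. At 49 kg, 600 − 12 × 49 = 12 mg/day below. The table's cut is 200 mg/day at both weights. Above 1200/12 = 100 kg in the 1200 mg band (up to 105 kg), and above 1400/12 = 116.7 kg in the top band, 12 mg/kg would exceed the starting dose. The sentence was evidently not written with these bands in view, yet nothing excludes them.

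**The case against.** The best counter-argument is that an ordinary reader would resolve this. The table gives the triggers, and the sentence gives the amount for children who started on 15 mg/kg. Alternatively, 200 mg is one capsule, so that cut belongs to the capsule bands of 47 kg or more. Either way a child under 47 kg would follow the sentence, and the extreme figures arise only if a site applies a capsule-sized cut to a small child on oral solution.

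Both readings are plausible, and they do agree under 47 kg. Neither is printed, however, and they contradict each other at 47 kg or more. On the first, the 200 mg/day in the column heading would apply to nobody in an all-pediatric trial. On the second, it applies to the heavier bands, although those subjects are also pediatric and may use the oral solution.

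A second argument is that the product label governs. Section 7.1 does say so, but it then presents Table 7-1 and its sentence as the information to use, so the deferral returns the reader to the conflict. Section 7.1 does not name the label. The supplied product is REBETOL (Section 5.3.1.1), while the ribavirin labels in the reference list are for COPEGUS.

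Some limits stand. No child under 13.3 kg is shown to be expected. Section 1.5 cites a figure for the expected weight range at 3 to <6 years, but its content is not in the text reviewed. The rule in Section 5.4 that "Study medications should not be cut or split" adds no separate conflict with the table, because 200 mg is one whole capsule. It would matter only if mg/kg steps were applied to subjects on capsules.

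**Conclusion.** The concern holds: the reduction guidance is wrong as written. For subjects under 47 kg the two printed instructions differ at every weight, by 200 − 3w mg/day, with the table always giving the lower dose. The 28.6 kg and 13.3 kg thresholds follow from the protocol's own figures and describe the table's cut taken literally. The finding does not depend on the 13.3 kg extreme.

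It assumes only that Table 7-1 and the sentence mean what they say, with no allocation rule elsewhere in the protocol. The number of subjects affected cannot be estimated: no anaemia rate or weight distribution is available in the text reviewed. No effect on SVR12, relapse or adherence is claimed. No view is taken on which reduction is clinically right.

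**What to change.** The sponsor should reconcile Sections 5.3.2 and 7.1 with Table 7-1 and the sentence beneath it, so that exactly one reduction instruction applies to every subject. The text should state which starting-dose bands and formulations each instruction covers, including subjects of 47 kg or more on oral solution. The choice belongs to the sponsor's clinical team.

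The cost is a protocol clarification letter or amendment text for one table and one sentence. No visits or procedures are added.

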### 7.2. Subject Stopping Rules for SOF

The Gilead Medical Monitor should be consulted prior to dose discontinuation of SOF unless the investigator believes that immediate action is warranted to ensure the continued safety of the subject.

Administration of SOF may be discontinued due to a clinical or laboratory event. There is no option for SOF dose reduction. If SOF is stopped for toxicity, it should not be restarted, RBV should be stopped and the subject should complete an Early Termination Visit.

Subjects who meet any of the following laboratory criteria must stop treatment with SOF and RBV:

- Elevation of ALT and/or AST >5x Day 1 or nadir, confirmed by immediate repeat testing
- Abnormal elevation of ALT >3x Day 1 and total bilirubin >2 x ULN, confirmed by immediate repeat testing
- Confirmed elevation of ALT >15 x ULN
- Any Grade 3 or greater rash associated with constitutional symptoms
- Any Grade 4 event or lab abnormality assessed as related to treatment with SOF

## 8. ADVERSE EVENTS MANAGEMENT

### 8.1. Definitions of Adverse Events, Adverse Reactions, and Serious Adverse Events

#### 8.1.1. Adverse Events

An adverse event (AE) is any untoward medical occurrence in a clinical study subject administered a pharmaceutical product, which does not necessarily have a causal relationship with the treatment. An AE can therefore be any unfavorable and/or unintended sign, symptom, or disease temporally associated with the use of a medicinal product, whether or not considered related to the medicinal product. AEs may also include pre- or post- treatment complications that occur as a result of protocol-mandated procedures, overdose, drug abuse/misuse reports, or occupational exposure. Preexisting events that increase in severity or change in nature during or as a consequence of participation in the clinical study will also be considered AEs.

An AE does not include the following:

- Medical or surgical procedures such as surgery, endoscopy, tooth extraction, and transfusion. The condition that led to the procedure may be an adverse event and must be reported
- Pre-existing diseases, conditions, or laboratory abnormalities present or detected before the screening visit that do not worsen.
- Situations where an untoward medical occurrence has not occurred (e.g., hospitalization for elective surgery, social and/or convenience admissions).
- Overdose without clinical sequelae (see Section 8.5)
- Any medical condition or clinically significant laboratory abnormality with an onset date before the consent form is signed and not related to a protocol-associated procedure is not an AE. It is considered to be pre-existing and should be documented on the medical history CRF

#### 8.1.2. Serious Adverse Events

A **serious adverse event** (SAE) is defined as an event that, at any dose, results in the following:

- Death
- Life-threatening (Note: The term “life-threatening” in the definition of “serious” refers to an event in which the subject was at risk of death at the time of the event; it does not refer to an event that hypothetically might have caused death if it were more severe.)
- In-patient hospitalization or prolongation of existing hospitalization
- Persistent or significant disability/incapacity

- A congenital anomaly/birth defect
- A medically important event or reaction: such events may not be immediately life-threatening or result in death or hospitalization but may jeopardize the subject or may require intervention to prevent one of the other outcomes constituting SAEs. Medical and scientific judgment must be exercised to determine whether such an event is reportable under expedited reporting rules. Examples of medically important events include intensive treatment in an emergency room or at home for allergic bronchospasm; blood dyscrasias or convulsions that do not result in hospitalization; and development of drug dependency or drug abuse. For the avoidance of doubt, infections resulting from contaminated medicinal product will be considered a medically important event and subject to expedited reporting requirements.

### **8.1.3. Clinical Laboratory Abnormalities and Other Abnormal Assessments as Adverse Events or Serious Adverse Events**

Laboratory abnormalities without clinical significance are not recorded as AEs or SAEs. However, laboratory abnormalities (e.g., clinical chemistry, hematology, and urinalysis) that require medical or surgical intervention or lead to IMP interruption, modification, or discontinuation must be recorded as an AE, as well as an SAE, if applicable. In addition, laboratory or other abnormal assessments (e.g., electrocardiogram, x-rays, vital signs) that are associated with signs and/or symptoms must be recorded as an AE or SAE if they meet the definition of an AE or SAE as described in Sections 8.1.1 and 8.1.2. If the laboratory abnormality is part of a syndrome, record the syndrome or diagnosis (e.g., anemia), not the laboratory result (i.e., decreased hemoglobin).

## **8.2. Assessment of Adverse Events and Serious Adverse Events**

The investigator or qualified subinvestigator is responsible for assessing AEs and SAEs for causality and severity, and for final review and confirmation of accuracy of event information and assessments.

### **8.2.1. Assessment of Causality for Study Drugs and Procedures**

The investigator or qualified subinvestigator is responsible for assessing the relationship to IMP therapy using clinical judgment and the following considerations:

- **No:** Evidence exists that the adverse event has an etiology other than the investigational medicinal product. For SAEs, an alternative causality must be provided (e.g., pre-existing condition, underlying disease, intercurrent illness, or concomitant medication).
- **Yes:** There is reasonable possibility that the event may have been caused by the investigational medicinal product.

It should be emphasized that ineffective treatment should not be considered as causally related in the context of AE reporting.

The relationship to study procedures (e.g., invasive procedures such as venipuncture or biopsy) should be assessed using the following considerations:

- **No:** Evidence exists that the AE has an etiology other than the study procedure.
- **Yes:** The adverse event occurred as a result of protocol procedures (e.g., venipuncture)

